Title: Time Limited Eating in Adolescents (Time LEAd): a Pilot Study

NCT Number: NCT03954223

Date of Document: 2/6/2023

Version: 7

PI: [name]

Center for Diabetes, Endocrinology, and Metabolism

Children's Hospital Los Angeles

Los Angeles, CA 90027

Overview of Study Design from Study Protocol:

The aim of this study will be to compare cardiometabolic effects of TLE (8-h eating period/16-h of daily fasting) versus a prolonged eating period (12+ h eating period) in a randomized pilot study with careful control of continuous adherence to prescribed eating window. This study was a prospective, randomized controlled pilot study in 50 adolescents (ages 14–18) with obesity (BMI% ≥ 95th percentile) recruited from clinical programs at Children's Hospital Los Angeles (CHLA). Patients will be randomized to one of three treatment groups for a 12-week intervention: Group 1): Control - Low sugar and carbohydrate educational intervention (LSC, < 5% of total daily calories from sugar/day; < 90 g carbohydrate (CHO)/day) + blinded CGM (used to monitor adherence and glycemic outcomes without real time feedback). Group 2): LSC + TLE (16-h fast/8-h feed for 5 days per week) + blinded CGM.

Table 3: Study Procedures and Measures

Weeks	0	4	12
Consent Completed	x		
Medical history	x		
Demographic Data	x		
CGM Education and equipment	x		
CGM (sensor change every 14 d, 12 w wear time)	x	x	x
Randomized	x		
Primary Outcomes			
Glycemic Control			
Percent Time in Range	x	x	x
Hemoglobin A1c	x	x	
Secondary Outcomes			
Nutrient Data System Recall: 24-hour dietary recall	x	x	
International Physical Activity Questionnaire	x	x	x
Pittsburg Sleep Quality Index and Chronotype Questionnaire	x	x	x
Monitoring for Adverse Events			
Dutch Eating Behavior Questionnaire	x	x	x
Binge Eating Disorder Screen	x	x	x

The implementation steps of the proposed study were as follows: (1) The staff introduced the study to all eligible participants either in person or virtually and consented interested families for the study; (2) All participants and their families completed a baseline study survey in REDcap; (3) All participants were trained to wear a blinded CGM using manufacturer educational materials under the supervision of research staff. Participants be changed the CGM sensor every 14 days for the duration of the study. During each study visit, the CGM reader was connected to the site database to create an individual participant report. All equipment required for the duration of the study was distributed to the participants at consent. Participants received enough sensors to wear the CGM daily for the entire study period. (4) All participants and their families received standard nutritional counseling and were randomized to one of three meal-timing schedules followed for 12 weeks: (1) Control or (2) TLE blinded CGM use, and (3) TLE real-time CGM use. During the eating window, participants were not required to count calories or monitor their food intake. Participants chose and paid for their own food during the intervention. All participants recorded their eating window daily and submitted it to the study staff via REDcap. All participants received standard recommendations for physical activity, screen, and sleep time as per the American Academy of Pediatrics age-appropriate recommendations at the first visit; (5) The study staff conducted study assessments with participants at week 0, 4, and 12; (6) The study staff performed weekly phone encounters with the participants to assess barriers to adherence and eating practices. If a barrier is identified the study staff created a solution plan to promote adherence and retention. The study staff recorded any medication changes or health issues that have occurred in the last 7 days. The PI reviewed CGM downloads collected at each study visit to ensure no treatment escalation is required; (7) To further inform future trials and scalability we collected continuously recruitment, consent, and retention rates, and barriers to engagement; (8) Adverse events were monitored. If at any time, the study staff noticed any unhealthy compensatory behaviors the PI was notified, and a treatment plan was created to ensure that the participant receive the appropriate screening, work-up, and diagnosis from their primary care provider and are withdrawn from the study if appropriate. (9) The PI and research team meet bi-weekly to monitor all study procedures and oversee data management and analysis.

Participants: We recruited 50 adolescents (age 14-18 years at enrollment, all gender expressions), with obesity. Inclusion criteria are: (1) age 14-18 years; (2) Tanner stage III and above; (3) obesity; (4) hemoglobin A1c ≤ 5.7%; (5) participant must be willing and able to adhere to the assessments, visit schedules, and eating/fasting periods; and (6) baseline eating window greater than 10 hours. To limit confounding factors, individuals will be considered ineligible to participate if they meet any of the following exclusion criteria: (1) diagnosis of Prader-Willi Syndrome, brain tumor or hypothalamic obesity; (2) serious intellectual disability; (3) previous diagnosis or subthreshold symptoms of an eating disorder (anorexia nervosa, bulimia nervosa, binge-eating disorder); (4) parent/guardian-reported physical, mental or other inability to participate in the assessments; (5) previous

bariatric surgery; (6) current use of an anti-obesity or other diabetes medication (e.g., phentermine, topiramate, orlistat, glucagon-like-peptide-1 agonist, naltrexone, bupropion, SGLT-2 Inhibitor, or insulin); or (7) current participation in other interventional weight loss studies. A random block stratified randomization scheme was used. Participants were randomized 1:1 via stratified, blocked randomization to ensure the groups were balanced in terms of number of participants and distribution of potential confounding variables including sex and age.

Retention strategies. To foster treatment adherence, participants received weekly calls from the study staff for the duration of the trial. Counseling was conducted by trained research staff. The sessions served three purposes: (1) foster adherence, retention, and accountability; (2) troubleshoot intervention barriers; and (3) monitor safety endpoints. To support participants, the staff will use behavioral techniques, such as stimulus control, goal setting, behavioral contracting, and motivational interviewing. In order to reduce participant burden, if at all possible study procedures will be scheduled to coincide with participants' scheduled clinical visits.

Intervention Arms:

Components Common to All Study Arms. All participants received two hours of standard nutrition counseling recommended for adolescents living with obesity. No specific caloric restriction was recommended. All participants maintained their usual lifestyle, including physical activity and sleep patterns. Physical activity and sleep recommendations consistent with the American Academy of Pediatrics guidelines for adolescents will be encouraged but not formally prescribed.

Time Limited Eating. The TLE intervention arm involved instructing participants to consume their usual kind and amount of food and beverages (all calories) within a pre-specified 8-hour period, fasting for the remaining 16-hours. They will be free to divide their food and beverage intake into as many meals or snacks as desired during the 8-hour period. We conducted a cross sectional analysis of a cohort of 100 adolescents with obesity and found that most total calories, carbohydrates, and added sugars were consumed between 11 AM and 8 PM.¹³⁶ In addition, in our feasibility trials, most adolescents selected an afternoon/evening eating window for both week days and weekend days, consistent with their shifting sleep/wake cycle and timing of social engagements.¹⁴ Therefore, to align with the normal developmental eating patterns seen in adolescents, we assigned an afternoon/evening TLE approach (consumption of all calories between 12:00 and 20:00 [plus or minus 1 hour] seven days per week). Participants allowed to consume non-caloric beverages (water, tea, coffee) during the fasting period. No energy restriction was required.

Control. Participants assigned to the control arm will be instructed to consume food over a 12-hour or more eating window. They were free to divide their food and beverage intake into as many meals or snacks as desired during the 12-hour period. No energy restriction was required.

Adherence Monitoring and Intervention Fidelity: To ensure differentiation between the intervention arms all participants recorded the time they start, and finish eating each day and provide their eating logs to the study staff weekly. Each week, study staff will determine the daily eating window for each participant by reviewing the time interval between the first and last caloric intake of the day. These self-reported time windows will be verified by examining the pattern of glucose excursions using the 24-h CGM data. If a participant adheres to meal timing protocol \leq 4 days/week, a follow-up call or videoconference will be scheduled to address challenges, give participants additional encouragement, support, and create a specific plan to promote adherence.

Continuous Glucose Monitor. All participants will be trained to wear a blinded continuous glucose monitor sensor using manufacturer educational materials under the supervision of research staff. Participants will be asked to wear the CGM for the duration of the study. During each study visit, the CGM reader will be connected to the site database to create an individual participant report. Participants will be provided enough sensors to replace the sensor every 14 days. The participants and guardians will be educated on how to use the CGM and receive 1:1 coaching on how to change the sensor, which will be completed either independently or under study team guidance. At each weekly phone meeting, study staff will monitor any challenges related to CGM wear, including participant discomfort, skin adherence, and other issues.

Measurements: The study team will conduct all assessments at week 0, 4, and 12. All data was collected and stored in REDCap.

Statistical Analysis Plan:

Primary Outcome—Feasibility

Compliance with the recommended eating windows was collected from adolescents during the weekly phone calls with the study team. Adolescents were asked to record the time they started and finished eating daily, the number of days they adhered to their prescribed eating schedule, and barriers to adherence. Adolescents were instructed to wear their CGM daily for the duration of the study and to report deviation from the protocol during the phone calls.

Secondary Outcome

Anthropometrics. All participants received a wireless Bluetooth scale upon consent. Participants' height and weight were collected by the participant and parent/guardian at home with the research coordinator monitoring the measurement collection via a HIPAA compliant virtual platform. Height was measured using a portable wall height indicator tape ruler, accurate to 0.5 cm (Posh Rulers, Quick Medical, Issaquah, WA). Weight was measured on a self-calibrating Etekcity Digital Body Weight Scale, accurate to 0.2 kg (Etekcity, San Diego, CA). Adolescents wore minimal clothing during the height and weight measurements. BMI was calculated as kilograms per meter squared excess percent of the 95th percentile (%BMIp95) was determined utilizing the CDC growth charts.

Continuous Glucose Monitoring

CGM data were downloaded weekly by the study team. CGM data were evaluated continuously over the study period. This data was utilized to compute the following measures: mean, maximum, and minimum glucose levels; standard deviation of glucose; mean amplitude of glycemic excursion; and overall percent of total time spent in euglycemic range (percent time in range = 70–180 mg/dL). All CGM data were housed in Clarity (Dexcom and Dexcom CLARITY are registered trademarks of Dexcom, Inc., San Diego, CA, USA) and the study team had weekly access to assess all glycemic excursions that occurred during the self-reported fasting periods [50–53]. For those in the TLE + real-time

Statistical Analysis

The study was a pilot trial, thus we opted for a convenient sample size of 50 participants to estimate parameters for a larger, fully powered trial. Analyses were based on the intention to treat (ITT) population using the last observation carried forward. The ITT population was defined as at least two visits (baseline and 1 month). The study was designed as a three-group intervention analysis; however, given that very few adolescents in the TLE+ real-time CGM feedback group looked at their real-time data, we completed a post hoc analysis combining both TLE groups compared to control for all analyses performed. Baseline characteristics (age, sex, race, BMI status, household income) were summarized descriptively across arms for the ITT population using mean and standard deviation (SD) or median and interquartile range as appropriate for the distribution of continuous variables. Categorical variables are described as a frequency and percentage. Continuous variables that are skewed were analyzed in log scale. The differences in demographics, anthropometrics baseline, and eating window distributions among intervention groups were examined using analysis of variance (ANOVA) and Fisher's Exact test. Adherence was operationalized as the number of days adolescents complied with their prescribed eating window, number of days they wore their CGM, and number of weekly phone calls and scheduled research visits they attended, and satisfaction scores were summarized using mean, standard deviation (SD), minimum, and maximum score between TLE and control. The TLE effect on mean change of %BMIp95 between week 0 and week 12 was assessed by using ANOVA. Then, a mixed-effects generalized linear model based on a Gaussian or Gamma distribution as appropriate was used to further assess the TLE effect on change in weight outcome from week 0 to week 12. The mixed-effects generalized linear model based on a Gaussian or Gamma distribution was used as appropriate for the distribution of continuous outcome variables. Whereas a mixed-effects logistic regression model was used for binary clinical outcome variables. In addition, a mixed effects Tobit regression model was used to evaluate the TLE effect on the change in quality- of-life assessment, where the scores are reported in percentages, with no data below 0 or above 100. Then, the non-additive effects of TLE were also examined; specifically, whether the change on clinical outcomes during the study period varied by intervention groups by including the interaction term in the mixed-effect models. In addition, sensitivity analysis was performed to examine whether the weight change observed in the data was influenced by one adolescent who achieved a weight loss of greater than 15% from baseline weight. All results are described in beta estimate, β , percent change, and odds ratio with its associated 95% confidence interval and p-value. The statistical

significance level was set at 0.05 with two-sided throughout the analyses. All statistical computations were done in Stata/SE 17.0 (StataCorp, College Station, TX, USA).

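### The weekly call's 7-day look-back has no catch-up rule, so general health issues and new medications arising in a missed week can go unrecorded

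*Combined protocol and SAP*

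**What the plan says.** Implementation step (6) sets the contact schedule: "The study staff performed weekly phone encounters with the participants to assess barriers to adherence and eating practices". The same step sets the look-back: "The study staff recorded any medication changes or health issues that have occurred in the last 7 days". The paragraph on retention strategies confirms that the calls run throughout ("participants received weekly calls from the study staff for the duration of the trial") and gives as the third of their three purposes to "monitor safety endpoints". Follow-up is 12 weeks (step (4): "randomized to one of three meal-timing schedules followed for 12 weeks").

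The Statistical Analysis section includes in its definition of adherence the "number of weekly phone calls and scheduled research visits they attended", summarised for TLE and control. No expected attendance rate is given.

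Other text that bears on safety ascertainment:

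- Step (8) states "Adverse events were monitored", without a form, method or look-back. It adds a path for compensatory eating behaviours that staff notice at any time.
- Table 3 lists two eating-behaviour instruments under adverse-event monitoring, at weeks 0, 4 and 12. Medical history appears at week 0 only.
- The Continuous Glucose Monitoring section has CGM data downloaded weekly, and step (6) has the investigator review the downloads collected at study visits.
- The adherence monitoring section adds a follow-up contact when a participant keeps to the meal timing on 4 or fewer days in a week.

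No section reschedules a missed call, lengthens the look-back after one, or asks about the time since the previous contact.

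**The concern.** A 7-day question asked every 7 days has no overlap. If a participant misses the week 6 call and answers in week 7, the question as written reaches back to the start of week 7, and week 6 is not asked about at any later call. The plan treats attendance as something that varies, so this is a foreseeable event.

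Most exposed are general illness and changes in medication, because the 7-day question is the only post-baseline route that the documents describe for them. Medication matters beyond safety. The exclusion criteria remove current users of anti-obesity and diabetes medicines in order to limit confounding, and the main clinical outcomes concern weight and glucose. A medicine started in a missed week could affect those outcomes and not appear in the record. The analysis also includes a sensitivity analysis around one adolescent with a large weight loss, and a complete medication history would help in reading a case of that kind. The pilot is meant to inform a larger trial, so an incomplete picture of harms would carry forward.

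**Working it through.** The documents state no adverse-event rate, expected count or attendance rate, so there is no figure of the plan's own to reproduce. What can be checked is coverage.

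**Inputs from the documents.** Look-back 7 days and weekly calls (step (6)); calls for the whole trial (retention strategies); 12 weeks of follow-up (step (4)); 50 participants (Statistical Analysis). I take weekly calls over 12 weeks to mean 12 calls, one at the end of each week.

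**Full attendance.** 12 × 7 = 84 days, the whole follow-up, with no overlap.

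**Assumed attendance.** Let *a* be the probability that a call is completed, independent from week to week.

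- Fixed 7-day look-back: covered share = *a*; uncovered days = 84 × (1 − *a*); uncovered person-weeks = 50 × 12 × (1 − *a*) = 600 × (1 − *a*).
- Look-back to the last completed contact: week *w* is covered if any call from *w* to 12 is completed, so covered share = (1/12) × Σ over *w* = 1 to 12 of [1 − (1 − *a*)^(13 − *w*)].

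| Assumed *a* | Uncovered days, 7-day rule | Uncovered person-weeks of 600 | Covered, 7-day rule | Covered, since last contact |
|---|---|---|---|---|
| 0.90 | 8.4 | 60 | 90% | 99.1% |
| 0.80 | 16.8 | 120 | 80% | 97.9% |
| 0.70 | 25.2 | 180 | 70% | 96.4% |

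The last column depends on misses being scattered. A participant who stops answering after call 8 is covered for 8/12 = 67% of follow-up under either rule, unless the question is also asked at the week 12 visit.

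**If attendance differs by arm.** With equal true rates and calls as the only route, the apparent TLE/control ratio is *a*(TLE)/*a*(control):

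- 0.80/0.90 = 0.89
- 0.70/0.90 = 0.78
- 0.90/0.80 = 1.13

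The ratio can fall on either side of 1. If other routes pick up a share *d* of events in missed weeks, coverage becomes *a* + (1 − *a*)*d*. For 70% against 90%:

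- *d* = 0.25: 0.775/0.925 = 0.84
- *d* = 0.50: 0.850/0.950 = 0.90 (0.895 before rounding)
- *d* = 0.75: 0.925/0.975 = 0.95

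With the look-back set to the last completed contact and no other route, the same 70% against 90% gives 0.9643/0.9907 = 0.97.

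**Which events the other routes can reach.** The Table 3 instruments address eating behaviour. CGM shows glucose. The detail in step (8) concerns compensatory behaviours that staff notice. The extra adherence contact carries no stated health question. None of these clearly reaches an intercurrent illness or a new prescription.

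**The case against.** The strongest reply is that the calls are not the only safety route. Eating-behaviour harm, a central worry with a fasting intervention, has its own scheduled instruments, glucose has continuous data, and step (8) is a separate if unspecific commitment. That stands, and it limits the point to what the calls alone would find. A reader might infer that all adverse-event counts fall in step with attendance, or that 20% of events are lost at 80% attendance. The documents do not support this: it sets detection by every other route to zero, and the 80% is itself an assumption.

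A reader might also infer a biased comparison between arms. No attendance figures are given, the direction is unknown, and the extra contact for low adherence could raise contact among those who struggle. The Statistical Analysis section specifies no adverse-event count, rate or test by arm, so there is no planned comparison to bias.

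It is also fair that a 7-day reference is an ordinary way to describe a weekly call. Nothing says that older events were refused or missed calls never made up, and no call script is included. Staff may have done better than the text. Even so, the text states a specific window and gives no instruction to go beyond it.

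Finally, much of the document is in the past tense and describes observed behaviour, so data collection appears to be over. Rewording the look-back now would misdescribe what was done. That limits the remedy for existing data but leaves the reporting step open.

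**Conclusion.** The point holds in a narrow form. Followed as written, each missed call leaves 7 days about which no later call asks. General health issues and medication changes in those days have no other described post-baseline route. The consequence is an incomplete description of safety and concomitant medication.

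The certain part is the 7 days per missed call. The totals (8.4 to 25.2 days per participant for attendance of 90% down to 70%) rest on assumed attendance and on the window being applied literally. The ratios by arm rest further on assumed differences in attendance, equal true rates and, at their most extreme, no detection by any other route. They show how sensitive a crude count would be and do not estimate what happened. The gap is worth closing because closing it is nearly free.

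**What to change.** **For calls still to be made, and for the larger trial.** In step (6), ask about medication changes and health issues since the last completed contact, and record the date of that contact. Ask the same question at the week 4 and week 12 visits, and add it to Table 3. The week 12 question closes the remaining gap for those who attend.

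**For data already collected under the 7-day question.** Leave the description of what was done unchanged. Report call-ascertained events and medication changes per covered week, together with calls attended, by randomised arm (all three arms, as well as the pooled TLE grouping). State that this rate assumes missed weeks resemble covered ones, which may fail if calls were missed because of a problem. If missed calls were in practice made up or older events accepted, say so.

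**Cost.** One phrase in the call script, one date field in REDCap, one added question at two visits and one descriptive table. Recall is slightly poorer over gaps of two weeks or more, but a less exact answer is better than no question.

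### Randomisation is stratified to balance sex and age, but no treatment-effect model is stated to include either; if they are prognostic, the unadjusted intervals are too wide (minor)

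*Combined protocol and SAP*

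**What the plan says.** All references are to the combined protocol and SAP.

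- **Participants.** "A random block stratified randomization scheme was used". "Participants were randomized 1:1 via stratified, blocked randomization", so that the groups would be alike in number and in the "distribution of potential confounding variables including sex and age". Age cut-points, number of strata and block size are not given.
- **Statistical Analysis, main test.** "The TLE effect on mean change of %BMIp95 between week 0 and week 12 was assessed by using ANOVA". No covariate is named.
- **Statistical Analysis, later models.** A mixed model "was used to further assess the TLE effect on change in weight outcome from week 0 to week 12". Logistic and Tobit mixed models cover other outcome types. The one extra term mentioned is an interaction, used to ask whether change during the study differed by group.
- **Where sex and age do appear.** They are in the descriptive baseline summary, and demographics are compared between groups at baseline.
- **Purpose.** "we opted for a convenient sample size of 50 participants to estimate parameters for a larger, fully powered trial".
- **Groups compared.** The trial had three groups, but "we completed a post hoc analysis combining both TLE groups compared to control for all analyses performed".

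**The concern.** Stratified blocks force the arms to be nearly alike on sex and age. Whatever those factors contribute to the outcome therefore largely cancels in the difference between arms. A one-way ANOVA does not know this: it counts the same variation as noise. When the factors are prognostic, the reported standard error is larger than the true one, the interval is too wide and the test rejects less often than its nominal 5%.

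Two things are at stake. The first is precision in a trial of 50, where a few per cent of interval width can be recovered from variables already collected. The second is the SD carried forward. The pilot exists to supply planning parameters, and a later trial analysed with adjustment for sex and age would need the adjusted residual SD, which the plan does not say it will report.

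**Working it through.** The plan gives no figure to reproduce: 50 is a convenience sample with no effect size, SD or power attached.

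**Inputs from the documents.** N = 50 (the analysed number may be smaller, because the ITT set requires a baseline and a 1-month visit). Two-sided 5%: "significance level was set at 0.05 with two-sided throughout the analyses". Stratified blocks on sex and age. Groups pooled as TLE versus control.

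**Assumptions.** R2, the share of outcome variance explained by sex and age, is taken from 0 to 30%. There are four strata (sex by two age groups). Both 2:1 allocation (three equal groups, two of them pooled) and 1:1 (as written) were run, because the stated ratio does not fit three groups. The results hardly differ.

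**Step 1: interval width by formula.** Adjusting for two 1-df factors leaves 46 rather than 48 error degrees of freedom. The ratio of unadjusted to adjusted width is

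t(0.975, 48) / [√(1 − R2) × t(0.975, 46)], with t values 2.0106 and 2.0129.

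At R2 = 20%: 2.0106 / (0.8944 × 2.0129) = 1.117.

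**Step 2: interval width by simulation.** Permuted blocks, 6,000 replicates per setting.

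**Step 3: SD and later sample size.** The ratio of unadjusted to adjusted SD is 1/√(1 − R2). Total N for a later two-arm trial scales with 1 − R2. It is illustrated with an assumed standardised effect of 0.5 and 80% power, which needs 126 in total on the unadjusted SD.

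| Assumed R2 | Width ratio, formula | Extra unadjusted width, simulated | SD ratio | Later N on adjusted SD (126 unadjusted) |
|---|---|---|---|---|
| 0 | 0.999 | about −0.3% | 1.000 | 126 |
| 2% | 1.009 | +0.7 to 0.8% | 1.010 | 124 |
| 5% | 1.025 | +2.4% | 1.026 | 120 |
| 10% | 1.053 | +5.2% | 1.054 | 114 |
| 20% | 1.117 | +12% | 1.118 | 102 |
| 30% | 1.194 | +19% | 1.195 | 88 |

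Simulation is slightly less favourable to adjustment than the formula because incomplete blocks leave some imbalance between arms.

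**Step 4: type I error of the unadjusted test.** With perfect balance it is about 2 × [1 − Φ(1.96/√(1 − R2))]. At R2 of 10%, 20% and 30% the cut-offs are 2.066, 2.191 and 2.343, giving 3.9%, 2.8% and 1.9%. With permuted blocks at 2:1, balance is incomplete. Simulated coverage of 95.6%, 96.8% and 97.7% implies 4.4%, 3.2% and 2.3%. A further run on the same assumptions gave 4.1%, 3.1% and 2.4%. The difference is Monte Carlo error: with 6,000 replicates its standard error near 4% is √(0.04 × 0.96/6,000), about 0.25 percentage points. At R2 of 5%, simulated coverage was 95.2% (2:1) and 95.6% (1:1). The adjusted interval stayed near 95% throughout (94.5% to 95.6%).

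**Step 5: how well 50 participants fix an SD.** Its relative standard error is about 1/√(2 × 49) = 10%. The SD ratio exceeds that only as R2 approaches 20%.

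These figures are for a linear model of change. They do not carry over to the logistic models.

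**The case against.** The strongest reply is that the loss depends wholly on an R2 the documents do not give, and that what they do say points low. The outcome is a within-person change over 12 weeks. %BMIp95 is referenced to growth charts, and participants are 14 to 18 years old and at Tanner stage III or above. At R2 of 2% or less nothing of consequence is lost. This stands, and it is why the range must start at zero. It is still inference, and for the plan's other outcomes no such referencing is described.

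A reader might draw four stronger conclusions that the documents do not support:

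- **That the intervals are too wide and the SD inflated, as fact.** Both depend on R2. The unadjusted SD is also the correct input for a trial analysed without adjustment.
- **That the larger trial would be oversized.** No analysis plan for it is given, nor any statement of which SD it will use.
- **That the mixed models leave sex and age out.** Their covariates are unstated. Model families are named, but no covariate list is given.
- **That no analysis uses either factor.** Both are summarised at baseline. The gap is confined to the treatment-effect models.

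It is also fair to say that the SAP makes feasibility primary and places anthropometrics under secondary outcomes, and that a conservative test adds no false-positive risk. This limits the severity. It does not remove the mismatch between how participants were randomised and how the effect is said to be estimated.

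**Conclusion.** The concern holds as a minor one. The design balances sex and age, and no treatment-effect model is stated to include them. If they are prognostic, unadjusted inference is conservative. Over the assumed R2 range of 0 to 30%, unadjusted intervals run from about 0.3% narrower to 19% wider than adjusted ones, and type I error falls from 5% to about 4.1%, 3.1% and 2.4% at R2 of 10%, 20% and 30%. This rests on four strata, permuted blocks at 2:1, N = 50 and a linear model. The lower end of the range is plausible for %BMIp95 change. Adjustment is worth making because it costs almost nothing if R2 is zero.

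**What to change.** 1. State the stratification factors with their age cut-points, and list the covariates of every treatment-effect model.
2. Replace the one-way ANOVA of %BMIp95 change with a linear model of change on group plus sex and age, coded as used to stratify.
3. Include the same terms in the mixed models for continuous outcomes. Where the effect of interest is the group-by-time interaction, let sex and age interact with time too, since main effects alone adjust the level and not the change. Add the factors to the logistic models only where event counts allow, and note that an adjusted odds ratio is not the same quantity as an unadjusted one.
4. Report both the unadjusted and the adjusted residual SD, so that the larger trial can take the one that matches its own analysis.
5. The section is written in the past tense, so label any adjusted results produced now as added.

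Cost: SAP wording, two variables already collected, and 2 to 3 degrees of freedom in the linear model (somewhat more where time interactions are added).
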